## 4.2 Exclusion criteria

Patients fulfilling any of the following criteria are not eligible for inclusion in this study. No additional exclusions may be applied by the investigator, in order to ensure that the study population will be representative of all eligible patients.

### Medical history and clinical status

1. Mixed *Plasmodium* infections
2. Signs and symptoms of severe malaria according to WHO 2015 criteria unless characterized by high parasitaemia only
3. Active infections including tuberculosis
4. Patients with concurrent febrile illnesses (e.g., typhoid fever)
5. History of, or current alcohol misuse/abuse defined as five or more drinks on the same occasion on each of 5 or more days in the past 30 days
6. Known relevant liver disease e.g. chronic hepatitis, cirrhosis, compensated or decompensated, history of hepatitis B or C, hepatitis B or A vaccination in last 3 months, known gallbladder or bile duct disease, acute or chronic pancreatitis
7. Any confirmed or suspected immunosuppressive or immunodeficient condition, including human immunodeficiency virus (HIV) infection
8. Severe malnutrition (body mass index (BMI) < 16.0 for patients  $\geq 12$  years, and less than 70% of median normalized WHO reference weight for children < 12 years)
9. Severe vomiting, defined as more than 3 times in the 24 hours prior to inclusion in the study or severe diarrhea defined as more than 3 watery stools per day
10. Pregnant or nursing (lactating) women
11. Sexually active patients not willing to practice effective contraception

12. Women of child bearing potential, defined as all women physiologically capable of becoming pregnant, unless they are using highly effective methods of contraception during dosing and for the duration of the study. Highly effective contraception methods include:
- Total abstinence (when this is in line with the preferred and usual lifestyle of the patient). Periodic abstinence (e.g., calendar, ovulation, symptothermal, post-ovulation methods) and withdrawal are not acceptable methods of contraception
  - Female sterilization (have had surgical bilateral oophorectomy with or without hysterectomy) total hysterectomy or tubal ligation at least six weeks before taking investigational drug. In case of oophorectomy alone, only when the reproductive status of the woman has been confirmed by follow up hormone level assessment
  - Male sterilization (at least 6 months prior to screening). For female patients on the study, the vasectomized male partner should be the sole partner for that patient
  - Use of oral, (estrogen and progesterone), injected or implanted hormonal methods of contraception or placement of an intrauterine device (IUD) or intrauterine system (IUS) or other forms of hormonal contraception that have comparable efficacy (failure rate < 1%), for example hormone vaginal ring or transdermal hormone contraception
- In case of use of oral contraception women should have been stable on the same pill for a minimum of 3 months before taking investigational drug
- Women are considered post-menopausal and not of child bearing potential if they have had 12 months of natural (spontaneous) amenorrhea with an appropriate clinical profile (e.g., age appropriate, history of vasomotor symptoms) or have had surgical bilateral oophorectomy (with or without hysterectomy), total hysterectomy or tubal ligation at least six weeks ago. In the case of oophorectomy alone, only when the reproductive status of the woman has been confirmed by follow up hormone level assessment is she considered not of child bearing potential
13. Sexually active males must use a condom during intercourse while taking drug and for the duration of the study and should not father a child in this period. A condom is required to be used also by vasectomized men in order to prevent delivery of the drug via seminal fluid
14. Active duodenal ulcer, ulcerative colitis, Crohn's disease, chronic (i.e., > 2 weeks) use of non-steroidal anti-inflammatory drugs (NSAIDs)
15. Clinically relevant abnormalities of electrolyte balance which require correction, e.g., hypokalemia, hypocalcemia or hypomagnesemia.
16. Anemia (Hemoglobin level < 8 g/dL)
17. Any surgical or medical condition which might significantly alter the absorption, distribution, metabolism, or excretion of drugs, or which may jeopardize the patient in case of participation in the study. The investigator should make this determination in consideration of the patient's medical history and/or clinical or laboratory evidence of any of the following:
- AST/ALT > 2 x the upper limit of normal range (ULN), regardless of the level of total bilirubin
  - AST/ALT > 1.5 and  $\leq 2$  x ULN and total bilirubin is > ULN

- Total bilirubin > 2 x ULN, regardless of the level of AST/ALT
- 18. Resting QTcF > 450 ms (males), QTcF > 460 ms (females) at screening
- 19. Creatinine > 2 x ULN in the absence of dehydration. In the case of dehydration, the creatinine should be < 2 x ULN after oral/parenteral rehydration
- 20. History of malignancy of any organ system (other than localized basal cell carcinoma of the skin or *in situ* cervical cancer), treated or untreated, within the past 5 years, regardless of whether there is evidence of local recurrence or metastases
- 21. Known chronic underlying disease such as sickle cell disease, and severe cardiac, renal, or hepatic impairment
- 22. Known active or uncontrolled thyroid disease
- 23. Inability to tolerate oral medication (in tablet and/or liquid form)

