### 6.5.5 Electrocardiogram (ECG)

ECGs should be taken in triplicate within 5 minutes (after 10 minutes rest in the supine position to ensure a stable heart rate according to the ECG investigator manual). The preferred sequence of cardiovascular data collection during study visits is ECG collection first, followed by vital signs, and blood sampling.

The Fridericia QT correction formula (QTcF) should be used for clinical decisions, except for children  $\leq 6$  years, when Bazett formula (QTcB) is recommended.

Triplicate 12 lead ECGs are to be collected with ECG machines supplied by the central laboratory. Initial manual readout will be done locally in order to detect significant safety findings and allow for immediate response if needed. Local readout will be used for inclusion/exclusion purposes as central readout is not available within 24 hours.

In the event that a clinically significant ECG abnormality is identified at the site (e.g., severe arrhythmia, conduction abnormality of QTcF > 500 ms) the SAE must be reported according to the procedure described in [Section 7.2](#). If the patient is hemodynamically compromised, the investigator or a medically qualified person must initiate appropriate safety procedures without delay (for example cardioversion).

If QTcF is > 500 ms or QTcF increases  $\geq 60$  ms from baseline occur at any time, the patient should be assessed at the site and appropriate safety procedures (e.g., electrolyte correction) initiated without delay, if required. In addition two additional ECGs should be collected at 2-min intervals and provided to the central ECG laboratory for confirmation.

Clinically significant abnormalities must be recorded on the relevant section of the medical history/Current medical conditions/AE eCRF page as appropriate.

For 2-3 day regimens, any post-dose average QTc  $\geq 500$  ms will result in patient discontinuation from the treatment if there is a planned subsequent treatment.

Assessments will be done as indicated in the study assessment schedule table. All ECGs will be assessed centrally by an independent and blinded (with age of patient identified) cardiologist.

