## 15 Appendix 3: Cardiac Alert Threshold Values and Actions

**Table 15-1 Cardiac alert threshold values and actions**

	Values	Actions
QTcF (QTcB for children ≤ 6 years) Cardiac rhythm	QTcB > 500 ms (< 6 years); QTcF > 500 (≥ 6 years). Sustained ventricular tachycardia lasting 30 sec or more, or ventricular fibrillation, or any hemodynamically compromising cardiac arrhythmia	If confirmed by two repeat ECG, check and correct the patient's serum potassium and magnesium immediately. Report as SAE to Sponsor and transmit to eRT immediately for prompt review. Discontinue patient from study therapy. Monitor ECG hourly until at least 2 consecutive hourly ECGs performed are back to baseline
QTcF (QTcB for children ≤ 6 years)  Resting heart rate	Increase from baseline ≥ 60 ms  HR < 50/min with > 25% decrease from pretreatment baseline verified by ECG	If confirmed by two repeat ECG, check and correct the patient's serum potassium and magnesium immediately. Report to Sponsor as AE (unless it meets the SAE criteria as described in Section 7.2.1 ) and transmit to eRT immediately for prompt review.

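### Exclusion 18 caps only QTcF, while the youngest Part B children stop treatment on QTcB 500 ms; Table 15-1 also gives a 6-year-old two formulas

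*Protocol*

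**What the plan says.** **Entry.** Exclusion 18 (Protocol Section 4.2) is "Resting QTcF > 450 ms (males), QTcF > 460 ms (females) at screening". It has no age split, and no QTcB entry limit appears anywhere. Section 4.2 opens by telling investigators not to add exclusions of their own.

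**Formula.** Section 6.5.5 uses QTcF for clinical decisions except at 6 years or younger, "when Bazett formula (QTcB) is recommended". The next paragraph says "Local readout will be used for inclusion/exclusion purposes".

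**Stopping and reporting.**
- Table 15-1 (Appendix 3): the row label is "QTcF (QTcB for children ≤ 6 years"), but the values in that row are "QTcB > 500 ms (< 6 years); QTcF > 500 (≥ 6 years"). The actions begin "If confirmed by two repeat ECG" and include "Discontinue patient from study therapy" and an SAE report.
- Section 6.5.5: "For 2-3 day regimens, any post-dose average QTc" of 500 ms or more stops treatment when a further dose is planned.
- Section 7.5: the same notable values, with QTcB at 6 years or younger.
- Section 5.7.2: QTcF above 500 ms on repeat ECGs, with a reference to Appendix 3.
- Appendix 1: QTcF above 500 ms on repeat ECGs, as an SAE-reporting value.

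**The concern.** The entry limit and the stop value are on different scales for the same child. Part B takes children from 2 years with fever or a recent history of it, so raised heart rates are plausible, and a raised rate pushes QTcB above QTcF. A child can satisfy exclusion 18 and already sit at or beyond the value at which treatment is to stop.

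In a Part B 2- or 3-day KAF156/LUM-SDF arm the first scheduled post-dose ECG is at 24 h, because Table 6-2 restricts the 6 h ECG in those arms to Part A. If QTcB has not fallen by then, the child loses the remaining doses and is reported as an SAE for a value that preceded dosing. Section 7.2.1 defines an SAE by appearance or worsening, but Table 15-1 writes no exception for an unchanged baseline.

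The second issue is independent of the first. A 6-year-old falls on both sides of the age cut within one row of Table 15-1.

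**Working it through.** **Inputs.** Entry limits 450/460 ms (exclusion 18). Stop value 500 ms (Table 15-1; Section 6.5.5). Upper normal resting heart rate 110 bpm for ages 1 to 6 and 95 bpm for the 6-to-12 row (SAP Table 2-3; the two rows meet at age 6). Rates of 120 and 140 bpm are my assumption for febrile children. The plan gives no conversion between the formulas, so there is no plan figure to reproduce for this step.

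**Step 1, relation.** QTcB = QT/RR^(1/2) and QTcF = QT/RR^(1/3), with RR = 60/HR. Hence QTcB = QTcF × (HR/60)^(1/6). The factor is 1.0796 at 95 bpm, 1.1063 at 110, 1.1225 at 120 and 1.1517 at 140.

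**Step 2, heart rate at which a child at the entry limit reaches QTcB 500 ms.** HR = 60 × (500/QTcF)^6.
- Girl at 460 ms: 60 × (500/460)^6 = 99.0 bpm, inside the SAP's normal range.
- Boy at 450 ms: 60 × (500/450)^6 = 112.9 bpm, just above it.

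**Step 3, eligible QTcF band that is already at or over QTcB 500 ms.**

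| Heart rate | QTcF at QTcB 500 | Girls (limit 460) | Boys (limit 450) |
|---|---|---|---|
| 110 bpm | 500/1.1063 = 452.0 | 8.0 ms | none |
| 120 bpm (assumed) | 500/1.1225 = 445.4 | 14.6 ms | 4.6 ms |
| 140 bpm (assumed) | 500/1.1517 = 434.2 | 25.8 ms | 15.8 ms |

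**Step 4, the 6-year-old in Table 15-1.** Under the row label the alert is QTcB above 500 ms, which is QTcF above 463.1 ms at 95 bpm or 452.0 ms at 110 bpm. Under the values cell it is QTcF above 500 ms. The wordings disagree over 500 − 463.1 = 36.9 ms and 500 − 452.0 = 48.0 ms.

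**Step 5, how often.** The documents do not say. I took 88 children under 6 (half of 175, assumed), mean QTcF 380 to 420 ms with SD 15 to 20, mean heart rate 115 to 145 bpm with SD 18, QTcF independent of heart rate, and half boys. Under these assumptions the simulated expected number entering above QTcB 500 ms runs from about 0 to about 23. At mean QTcF 400 ms, SD 20 and 125 bpm it is 2.1. The range is too wide to support a number.

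**Step 6, effect on the per-protocol set.** A stop before dose 2 leaves 1/2 = 50% or 1/3 = 33% of doses, below the 80% required. The plan inflates 42 to 42/(1 − 0.16) = 50 per arm, so it already allows for 8 losses.

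**The case against.** The strongest reply is that the protocol is more coherent than a rule-by-rule comparison suggests. A reader might infer that the stopping rules conflict throughout, with the 2-3 day rule lacking both formula and confirmation. The text does not support that:
- Section 6.5.5 has already set the formula for clinical decisions, and stopping treatment is one. Its rule acts on an average, and ECGs are taken in triplicate. It is a stricter extra layer.
- Section 5.7.2 cites Appendix 3, where the QTcB value stands.
- Appendix 1 lists what to report and does not cancel Table 15-1.
- Section 7.5 sends every event to Table 15-1.

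What remains is the age contradiction inside Table 15-1. In a multi-day arm a 6-year-old may be stopped under Section 6.5.5 in any case, which softens it. But that section only recommends QTcB, and the confirmation, reporting and monitoring steps are in Table 15-1.

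On entry, Section 6.5.5 could be read as applying QTcB at screening, and exclusions 15, 17 and 28 give some room for electrolyte problems, jeopardizing conditions and QT-prolonging conditions. It would therefore be wrong to say that investigators have no discretion. None of these supplies a QTcB number, however, and exclusion 18 names QTcF.

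A QTcF entry limit in febrile children is also defensible. Moving 450/460 ms onto QTcB would be equivalent at 110 bpm to QTcF 406.8/415.8 ms. In the mid-range scenario of Step 5 it would exclude about 44% of these children. That argues against transferring the limits, and leaves room for a separate cap.

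Finally, the harm needs several things together: QTcF near the limit, a raised rate, a multi-day arm, and persistence to 24 h. If the heart rate settles, nothing follows. A 1-day arm has no later dose to lose. All of this stands and keeps the point small.

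**Conclusion.** Two narrow points hold. First, on the literal text a young Part B child can enter at or above the QTcB value at which treatment stops: a girl at QTcF 460 ms above 99 bpm, a boy at 450 ms above 113 bpm. Second, the values cell of Table 15-1 contradicts its own row label and Sections 6.5.5 and 7.5, so a 6-year-old's ECG can be an alert or not over 37 to 48 ms of QTcF.

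The first rests on the Bazett and Fridericia definitions and on reading exclusion 18 as written. The wider bands in Step 3 also rest on assumed febrile heart rates. A reader might infer that a definite number of children would be affected, or that the primary analysis is threatened. The documents give no frequency, and the losses allowed for in the sample size leave room for a few such stops. I claim no effect on power, error rate or the primary result. The point is minor: a child-safety and consistency matter that wording can settle.

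**What to change.** 1. In the Table 15-1 values cell, use QTcB for children aged 6 years or younger and QTcF above 6 years. This follows the row labels and Sections 6.5.5 and 7.5. Choosing under 6 instead would match the randomization stratum but would take the QTcB alert away from 6-year-olds.
2. In Section 5.7.2 and Appendix 1, add after QTcF: *(QTcB for children ≤ 6 years)*.
3. Leave the Section 6.5.5 rule for 2-3 day regimens as it is. Replacing it with a value above 500 ms plus two repeats would loosen a safeguard.
4. Keep the QTcF limits in exclusion 18 and add: *in children ≤ 6 years, also mean QTcB ≥ 500 ms on the screening triplicate ECG*.

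**Cost.** These are wording changes only. QTcB comes from the screening ECG already taken, and SAP Section 2.8.3.1 already summarizes both corrections, so no test, visit or analysis is added. A small, unknown number of febrile, tachycardic young children would be excluded. Because the cap sits at the stop value, a child just under 500 ms at entry can still cross it later. The change reduces the problem without removing it. A lower cap would add margin but exclude more children: QTcB 480 ms corresponds to QTcF 480/1.1063 = 433.9 ms at 110 bpm.

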### Interfering substances

- 24. Patients with prior antimalarial therapy or antibiotics with antimalarial activity within minimum of their five (5) plasma half-lives (or within 4 weeks of screening if half-life is unknown)
- 25. Use of other investigational drugs within 5 half-lives of enrollment, or within 30 days or until the expected pharmacodynamic effect has returned to baseline, whichever is longer
- 26. Patients taking medications prohibited by the protocol (see [Section 5.6.8](#), [Table 5-5](#))
- 27. Previous participation in any malaria vaccine study or received malaria vaccine in any other circumstance

### Specific to the study

- 28. History or family history of long QT syndrome or sudden cardiac death, or any other clinical condition known to prolong the QTc interval, such as history of symptomatic cardiac arrhythmias, clinically relevant bradycardia or severe heart disease
- 29. Use of agents known to prolong the QT interval unless it can be permanently discontinued for the duration of study
- 30. History of hypersensitivity to any of the study drugs or its excipients or to drugs of similar chemical classes

## 5 Treatment

### 5.1 Study treatment

#### 5.1.1 Investigational and control drugs

Novartis will supply the following investigational products as open label patient specific supplies (see [Table 5-1](#), [Table 5-3](#), [Table 5-4](#) and [Appendix 5](#)).

- For PK Run-in Part:
  - KAF156 50 mg and/or 100 mg and/or 200 mg (Tablets in bottles)
  - Lumefantrine 480 mg (SDF in sachets)

- For Part A:
  - KAF156 100 mg and/or 200 mg (Tablets in bottles)
  - Lumefantrine 480 mg (SDF in sachets)
  - Coartem® 20/120 mg and 80/480 mg (tablets in blister pack)
- For Part B:
  - KAF156 (Tablets in bottles). Dose strengths based on [Table 5-4](#) to be confirmed
  - Lumefantrine (SDF in sachets). Dose strengths based on [Table 5-4](#) to be confirmed
  - Coartem® 20/120 mg (dispersible tablets in blister pack)

**Table 5-1 PK Run-in Part: KAF156 and LUM-SDF dosing scheme**

Cohort	Treatment	Dose (mg)	Dosing regimen	Daily dosing based on available strengths
PK Run-in	KAF156	200	QD 1 day	1 x 200 mg or 2 x 100 mg 2 sachets
	LUM-SDF	960		

**Table 5-2 Part A: KAF156 and LUM-SDF dosing scheme\***

Cohort	Treatment	Dosing regimen
1	KAF156	QD 1 day
	LUM-SDF	
2	KAF156	QD 1 day
	LUM-SDF	
3	KAF156	QD 2 days
	LUM-SDF	
4	KAF156	QD 3 days
	LUM-SDF	
5	KAF156	QD 3 days
	LUM-SDF	
6	KAF156	QD 3 days
	LUM-SDF	

\*KAF156 dose levels are based on the results of the PK Run-in Part and will be adjusted according to [Table 3-1](#) (see also Appendix 5 for dosing details).

**Table 5-3 Parts A and B: Coartem® dosing per weight**

	Artemether/Lumefrantrine
≥ 12 years and ≥ 35.0 kg	80/480 mg BID during 3 days
25.0 to < 35.0 kg	60/360 mg BID during 3 days
15.0 to < 25.0 kg	40/240 mg BID during 3 days
10.0 to < 15.0 kg	20/120 mg BID during 3 days

**Table 5-4 Part B: Children KAF156 and LUM-SDF dosing per weight**

	KAF156 and LUM-SDF
25.0 to < 35.0 kg	0.75 of the adult dose
15.0 to < 25.0 kg	0.50 of the adult dose
10.0 to < 15.0 kg	0.25 of the adult dose

The selected adult doses from Part A will be adjusted to the pediatric population in Part B using the proven body weight bands for Coartem®. Specific details on medication will be communicated to relevant internal and external stakeholders before the start of Part B.

### 5.1.2 Additional treatment

No additional treatment beyond investigational drug and control drug are included in this trial. Rescue medication will be provided by the investigator according to local practices (Section 5.6.6).

## 5.2 Treatment arms

Following confirmation of exposure in the PK Run-in Part, patients will be randomized in 2:2:2:2:2:2:1 ratios between six KAF156 and LUM-SDF dose combinations and the Coartem® cohort in Part A. In Part B, patients will be randomized in 2:1 ratios (2 for each KAF156 and LUM-SDF dose combination and 1 for Coartem) to one of up to three KAF156 and LUM-SDF dose combinations and the Coartem® cohort depending on the outcome of Part A interim assessment.

### PK Run-in Part ( $\geq 12$ years old, $\geq 35.0$ kg):

- PK Run-in Cohort: KAF156 200 mg and LUM-SDF 960 mg - QD for 1 day

### Part A ( $\geq 12$ years old, $\geq 35.0$ kg)\*:

- Cohort 1: KAF156 400 mg and LUM-SDF 960 mg - QD for 1 day
- Cohort 2: KAF156 800 mg and LUM-SDF 960 mg - QD for 1 day
- Cohort 3: KAF156 400 mg and LUM-SDF 960 mg - QD for 2 days
- Cohort 4: KAF156 200 mg and LUM-SDF 480 mg - QD for 3 days
- Cohort 5: KAF156 400 mg and LUM-SDF 480 mg - QD for 3 days
- Cohort 6: KAF156 400 mg and LUM-SDF 960 mg - QD for 3 days
- Cohort 7: Coartem® BID for 3 days

\*KAF156 dose levels are based on the assumption of non-significant drug-drug interaction in the PK Run-in Part and will be adjusted according Table 3-1 in case of increased exposure to KAF156 in the PK Run-in cohort.

### Part B (2 to < 12 years, $\geq 10.0$ kg):

- KAF156 and LUM-SDF (up to 3 cohorts selected depending on the outcome of Part A)
- Coartem® BID for 3 days

## **5.3 Treatment assignment and randomization**

### **PK Run-in Part**

At Visit 101, the investigator or his/her delegate will contact the IRT after confirming that a patient fulfills all the inclusion/exclusion criteria. If the enrollment for this part is still open, the eligible patient will be assigned to receive KAF156 200 mg and LUM-SDF 960 mg QD 1 day via Interactive Response Technology (IRT). The IRT will specify medication number(s) and amount (e.g., number of tablets, etc.) to the patient. The medication number(s) and the appropriate amount for each medication number will be communicated to the caller so that the corresponding investigational drug(s) can be dispensed to the patient.

### **Parts A and B**

Following completion of the PK Run-in Part, at Visit 101, all eligible patients will be randomized via Interactive Response Technology (IRT) to one of the treatment arms. The investigator or his/her delegate will contact the IRT after confirming that the patient fulfills all the inclusion/exclusion criteria. The IRT will assign a randomization number to the patient, which will be used to link the patient to a treatment arm (cohort) and will specify medication number(s) and amount (e.g., number of tablets, etc.). The medication number(s) and the appropriate amount for each medication number will be communicated to the caller so that the corresponding investigational drug(s) can be dispensed to the patient. The randomization number will not be communicated to the caller.

The randomization numbers will be generated using the following procedure to ensure that treatment assignment is unbiased and concealed from Novartis Clinical Trial Team. A patient randomization list will be produced by the IRT provider using a validated system that automates the random assignment of patient numbers to randomization numbers. These randomization numbers are linked to the different treatment arms, which in turn are linked to medication numbers. A separate medication list will be produced by or under the responsibility of Novartis Drug Supply Management using a validated system that automates the random assignment of medication numbers to packs containing the investigational drug.

The randomization scheme for patients will be reviewed and approved by a member of the Randomization Group. Randomization will be stratified by country in Part A and by country and age category at screening in Part B (2 to < 6, 6 to < 12 years).

